TC visits will recognize and normalize the challenges of T1D care, and use constructive, family-centered communication, active problem solving regarding behavioral barriers to optimal T1D care, and negotiated problem solving plans to achieve families' T1D goals. TC team members will be trained in Motivational Interviewing to enhance their patient-centered communication skills. The TC Psy. Fellow will assure that problem solving plans or behavioral interventions are appropriate to the adolescent's developmental status, that family-team negotiations yield measurable, achievable, and sustainable short-term goals and that these plans are documented carefully in the EMR. The final TC model is likely to have certain features, including extensive sharing of discipline-specific knowledge and skills among team members, reduced frequency of MD contacts with TC patients, conjoint involvement of all TC team members during TC visits, psychosocial

screening of all TC patients and families at study entry, active reliance on motivational interviewing, patient-centered communication, shared medical decision making and negotiated goal setting during visits, and use of a “toolbox” of low-intensity behavioral interventions targeting common behavioral barriers to care. Family handouts and guides developed in behavioral intervention trials will be used with TC families.^{206-228,275} Results of study questionnaires may lead to referrals for further assessment or intervention external to the study.

The TC team who will see each family together will not include Social Workers or Diabetes Educators. This decision was based on concerns revealed in our preliminary studies that too many professionals would be overwhelming to families, cumbersome logistically and too expensive for this mechanism. Services of these professionals can be considered a “given” in any well-resourced T1D clinic and will be available to all study participants. The decision to exclude them from the TC teams will be re-visited with the Adolescent and Parent Crowds in Year 1 of the proposed work.

Transdisciplinary Care: In Person (TC-IP) versus Telehealth (TC-TH) Delivery TC-IP involves face-to-face sessions with the TC team meeting together with the family at the diabetes clinic. TC-TH will be the same as TC-IP except T1D visits will occur with families at their homes or other remote location via a HIPAA-compliant telehealth platform such as American Well AW9 (<https://www.americanwell.com/aw9-launched-at-himss/>). This platform has been used by Nemours CareConnect in Florida since 2015 and in Delaware since May, 2016. Patients/parents can access CareConnect from any PC, Apple or Android device. Technical support from Nemours Telehealth is budgeted.

FIGURE 2. STUDY DIAGRAM OF REVISED RANDOMIZED CONTROLLED TRIAL

Changes to Experimental Design and Treatment Conditions related to COVID-19 Precautions In March of 2020, Nemours began transitioning all T1D clinical care visits to telehealth as a precaution against spread of the novel coronavirus, COVID-19. About one third of the families randomly assigned to TC-IP had completed the study. Those randomized to TC-IP and part way through the study and those recently randomized to TC-IP were not able to complete face-to-face visits. After considering the options of: 1) halting delivery of all TC care across all arms of the study until in person care was possible again; and, 2) providing TC-IP families with TC delivered through telehealth, our study DSMB recommended the latter. Because we could not predict when in person visits would again be allowed and suspending TC care would result in a smaller “dose” of the experimental treatment, the option to alter delivery mode was chosen to gather as much information as possible about the potential efficacy of TC and to explore additional questions about mode of delivery (e.g., feasibility, family preference).

Families who had already received some TC-IP visits were transitioned to receiving TC through telehealth and were reclassified as “TC-IP/TH.” Those randomized to TC-IP who had received no TC-IP visits but were due for clinical care also received TC through telehealth and moving forward will be allowed to choose (to the extent allowed by precautions) whether they want to receive TC visits in person or remain with telehealth. They are being tracked as “TC-TH/CH.” See Figure 2 above. Because these new arms of the study will be small and combine IP and TH delivery of TC, all TC arms of the study will be combined for primary comparisons against UC and comparisons will be made between the TC groups (size permitting) to explore whether delivery mode is important for outcomes. It is important to note that UC appointments are, for now, also being delivered through telehealth. This previously available option for UC was not widely used.

TC Team Training: An optimal test of TC requires that team members have requisite knowledge, skills and practical experience at trial initiation. Careful training also promotes integrity of the TC arms of the study. Key elements of TC are sharing of knowledge and skills among disciplines and lowering of inter-professional boundaries. TC team training will comprise: 1.) Knowledge of TC and its distinction from other models; 2.) Teaching one another about the evidence base and clinical practices for each of the team’s professions; and 3.) Experiential learning in applying TC with simulated patients and then actual clinical cases. Reaching agreement on what comprises TC is also a prerequisite to achieving it in the RCT. TC team members will discuss directed readings,^{282,283} categorize hypothetical programs as Multi-, Inter- or Trans-Disciplinary models, and interview colleagues about T1D care at their institutions and evaluate them from a TC perspective. Qualitative interviews of team members during the RCT will guide refinements to TC training and implementation, yielding an empirically validated TC curriculum for future RCTs.

Team members will collaborate on a curriculum for teaching the others about their disciplines, with content guided by diabetes organizations.^{282,283} The researchers will develop test items for a TC Knowledge Test covering the knowledge base of each discipline, such as sample items from CDE Certification Exam practice tests on managing T1D in adolescents. As was done for another of [name] NIH grants, training will include two full-day experiential seminars at a one-month interval offered by a Certified Motivational Interviewing Trainer, to equip the TC team members with key MI skills. Practical experience will be gained in the following month and the team will audio-record simulated or real clinical interactions for review at the 2nd session. Team members will practice these skills in their clinical work and give each other feedback to refine these skills. Once each team member achieves a score of $\geq 90\%$ on the TC Knowledge Test, the curriculum will turn to experiential, team-building activities to equip the team members to co-manage patients with T1D, first with “simulated” and later with real clinical cases, including both face to face and telehealth delivery experience. Several of [name] staff are experienced simulated patients/parents. These sessions will involve the TC team conducting a simulated clinic visit with a “patient” and a “parent”. Once the TC team has gained comfort with simulated patients, they will extend this to the care of a few T1D patients who are ineligible for the RCT. TC teams will collaboratively evaluate clinical problems and negotiate problem solving plans with families. Evaluation of TC training will consist of scores on the TC Knowledge Test for each HCP and two qualitative interviews, once at the end of training and again after 1 year of TC experience. These data will guide refinement of the TC curriculum and manual for training HCPs in TC delivery in a future multi-site trial.

Prevention of TC-UC Contamination: Treatment integrity and internal validity of the RCT will be optimized by minimizing intrusion of TC elements into UC visits. We seek to prevent receipt of elements of the TC model of care during UC visits, including seeing multiple HCPs simultaneously, use of motivational interviewing or problem solving communication training methods during visits, receipt of behavioral and psychological interventions that are explicitly integrated with the patient's T1D care and education, and the intentional blurring of professional roles that are critical to the TC model. More TC teams would be ideal, but not affordable. Adolescents will be ineligible for the study if they have had one or more T1D clinic visits in the prior year that mimic TC (More than one health care provider seeing the adolescent concurrently) UC patients will continue to see their established HCPs. Thorough training of study clinicians about the need to segregate the TC and UC arms will further reduce contamination. A post-visit checklist completed by parents and a post-study questionnaire completed by HCPs providing care in the past year to study participants will assess the extent to which contamination occurs. Feedback to, or retraining of, project staff will be done if necessary. We will verify via EMR documentation any UC visits that include instances of multiple clinicians seeing the patient/family together. UC patients/families needing psychological services will be referred to psychologists who are not TC team members. We will document any psychological or psychiatric interventions received by UC patients outside of the study. It would be unethical for the researchers to constrain UC patients from receiving needed mental health interventions outside of the study.

Measurement Schedule and Protocol:

Measures will be obtained at clinic visits at Baseline and ~quarterly for 1 year. Primary outcomes are change in HbA_{1c} and the Diabetes Self Management Profile Self-Report Form total score over 1 year. Other planned measures will be reviewed and refined by the Adolescent and Parent Crowds during RCT planning. To promote retention, encourage timely completion of questionnaires and minimize missing data, each adolescent will receive \$40 credited to a gift card when all measures scheduled for a given study visit are completed. Also, adolescents will receive a \$10 bonus if they complete all of the questionnaires within 7 days of the research team's e-mail containing a link to the REDCap platform for questionnaire administration at Baseline, 6 and 12 months. Online completion of questionnaires will be available for those with internet access using REDCap. Those who do not complete questionnaires online before visits can do so at visits via PC, tablet or hard copy or online during TC visits. Table 3 shows the measurement schedule, including estimated participation burden per measure. Respondents are indicated by A (Adolescent), P (Parent) or HCP (Health Care Provider). Participation burden has been minimized in several ways. Questionnaire completion is limited to study visits at 0, 6 and 12 months rather than every quarterly visit. Questionnaire completion time at the Baseline visit is 75-80 minutes for parents and adolescents and 65-70 minutes at 6 and 12 months. Online completion of questionnaires via REDCap can minimize inconvenience by enabling participants to complete questionnaires at convenient times or over several distinct periods.

Table 3. Measurement schedule.

Measures	Burden (Min/Visit)	~Quarterly Clinic Visits				
		0	3	6	9	12
Demographic Information (P)	10	•				
HbA _{1c} ; Device downloads; Glycemic variability; Hypoglycemia Diary (A,P)	20	•	•	•	•	•
Appointment keeping; Health Care Use, Costs, Time expended (P; EMR)	5	•	•	•	•	•
Type 1 Diabetes and Life Measures (A,P)	15	•		•		•
Diabetes Self Management Profile-Self Report (A,P)	15	•		•		•
Problem Areas in Diabetes Scale (A,P)	15	•		•		•
Collaborative Parent Involvement Scale (A)	5	•		•		•
Family-Centered Care Self-Assessment Tool (A,P)	10	•		•		•
Diabetes-Specific Risk-Taking Inventory (A)	10	•		•		•
Readiness Assessment for Emerging Adults with Diabetes Diagnosed in Youth (A)	5	•		•		•
Diabetes Care Inventory (HCP)	5					•

Demographic information: This form records child and parent age, gender, race, ethnicity, family composition, education, occupational category, socioeconomic status²⁸⁴ and certain details of the child's medical history. Adolescents will be asked if wish to provide their cell phone numbers to permit text message reminders from the research team about questionnaire completion. It will be made clear that this is entirely optional.

Glycohemoglobin (HbA_{1c}): will be measured at the NCH or AIDHC labs, or at insurer-mandated labs certified by the National Glycohemoglobin Standardization Program, to index recent glycemic control.^{285,286} TC-TH patients can do this at many Nemours satellite clinics so results will be available at visits.

Device downloads: Youth will receive \$5 credited to a gift card for downloading a glucose meter, insulin pump or continuous glucose monitor prior to each study visit. These data will quantify monitoring frequency/use, mean and SD of blood glucose, mean daily glycemic excursions, other glycemic variability measures²⁸⁷⁻²⁸⁹ and, for insulin pump users, mean daily frequency of premeal bolus infusions.

Hypoglycemia Diary: This measure, used in [name] recent studies, records episodes of moderately severe hypoglycemia (requiring help) or severe hypoglycemia (with seizure or loss of consciousness). This will be submitted by parents via REDCap just after each study visit.

Health care use, costs and time expended: At each visit, parents will complete a form used in the JDRF CGM trial for tracking health care use and costs to capture direct and indirect costs of the youth's care.^{290,291} We will use EHR data to measure the interval between electronically recorded check-in (or login for TC-TH) and check-out times (logout for TC-TH). Parents will also estimate time expended for each visit, including travel.

Diabetes Self Management Profile-Self Report Version (DSMP-SR): Among T1D adherence measures,²⁹²⁻³⁰² the 24 item DSMP-SR assesses self-care behaviors that typify current T1D care and it has a mean correlation of .48 with HbA_{1c}, α of .79 and parent-youth correlation of .63.²⁹⁷⁻³⁰⁰

Type 1 Diabetes and Life (T1DAL) Measures: Separate versions of this quality of life questionnaire³⁰³⁻³⁰⁴ have been developed for 8-11 year olds with T1D (36 items), 12-17 year olds with T1D (44 items), parents of 8-11 year olds with T1D (47 items) and parents of 11-17 year olds with T1D (50 items). Empirically derived condensed versions of these instruments are undergoing validation.

Problem Areas in Diabetes Scale (PAID): (Teen and Parent brief versions). Respondents rate their agreement with 14 (Teen) or 15 (Parent) statements related to their worry and burden about their diabetes.³⁰⁶⁻³⁰⁸ Items are rated on a 6-point scale from "not at all" to "serious problem", and higher scores reflect less perceived burden/worry. Wasserman et al.³⁰⁹ recently validated the condensed versions of both scales.

Diabetes-Specific Risk-Taking Inventory (DSRI): The DSRI is a 34-item adolescent report measure that assesses the frequency with which adolescents (ages 15-18) engage in diabetes-specific risk-taking behaviors.³¹⁰ Adolescents report the frequency of each behavior on a 5 point likert scale, with the options of "Daily (5), Weekly (4), Monthly (3), Every few months (2), Yearly (1), Never (0), and Not Applicable." A mean score is used, with a higher score indicating more frequent diabetes-specific risk-taking behavior. In a validation study with 224 adolescents, the DSRI demonstrated excellent internal reliability ($\alpha = .90$).

Family-Centered Care Assessment (FCCA): The FCCA³¹¹ is a consumer-driven measure of the degree to which medical care received for a specific medical condition achieves ten accepted principles of family centered care. There are parallel, validated, 24-item forms for completion by parents and adolescents.

Collaborative Parent Involvement Scale (CPI): The 12-item CPI obtains youths' level of teamwork in T1D care with a specified adult.¹⁵⁷ Those living with two parents will complete the CPI separately about each. Higher total scores indicate that the youth perceives more T1D collaboration with that caregiver. Cronbach's α was .93 and .96 for youths' ratings of primary and secondary caregivers, respectively.

The Readiness Assessment for Emerging Adults Diagnosed with Diabetes in Youth (READDY): The READDY is a 13 item self-assessment of adolescents' readiness to transfer from pediatric to adult care for T1D. The scale has been validated by researchers at Cincinnati Children's Hospital and Children's Hospital of Seattle and a publication reporting these findings is under editorial review at this time.

Diabetes Care Inventory (DCI): This 17 item scale was developed by the research team to assess the nature of diabetes care provided to each participant in the study and to gauge the extent to which elements of Transdisciplinary Care are being provided to participants. Completed by healthcare providers, the measure includes questions regarding the provider's approach to care (i.e., use of motivational interviewing), the extent of their collaboration with providers outside of their discipline, the nature of their communication with other providers, and the format of care visits (e.g., multiple providers in the room at the same time). Aspects of the measure are based upon a provider-completed measure of use of motivational interviewing techniques.³¹² The DCI will be completed by all endocrinologists, nurse practitioners, dietitians, social workers, and psychologists seeing the patient during the course of the study (identified through the patient's EHR) after the final study visit for each enrolled adolescent.

Post-RCT Qualitative Interviews: These interviews (See Appendix) will obtain parent/adolescent views of the TC process, factors affecting its efficacy, advantages/disadvantages of the model, and suggested refinements. Qualitative interviews of representatives of third party payers will seek their views of the viability of the TC model, based on the RCT results and costs relative to UC. Audio recordings of interviews will be transcribed verbatim and coded by trained coders under the supervision of [name].

Analytic Plans Primary endpoints are change in HbA_{1c} and DSMP-SR total score (treatment adherence) over 1 year. Secondary endpoints are: # of severe hypoglycemic events (Hypoglycemia Diary); measures of glycemic variability at each visit; and questionnaires obtained quarterly. The Full Analysis Set will include those who provide data at ≥ 1 follow-up visit. The Completer Analysis set will include those who provide data at all follow-ups. Efficacy analyses will be done on both sets.³¹³⁻³¹⁵ We will use multiple imputation for treatment of missing data.³¹³⁻³¹⁵ Obtained data will be summarized in graphs and tables. Categorical variables will be summarized by frequencies and percentages; continuous variables by mean, median, standard deviation (or SEM), minimum and maximum. Data will be summarized by primary group (UC and TC), secondary group (TC-TH, TC-IP, TC-IP/TH, TC-TH/CH) and measurement points.^{316,317} Model assumptions will be checked before analyses, and appropriate transformations or non-parametric methods will be used when indicated. For summarization of normally distributed data, group means and SEM will be presented. In case of substantial deviation from normality, boxplots will be presented. Exploratory subgroup analyses (e.g. race, ethnicity, gender, SES, secondary group) will be conducted as needed.^{318,319} Most tests will be performed against a two-sided alternative at the $\alpha = 0.05$ significance level and a 95% confidence interval and/or a p-value will be provided for inferential purposes. Data from both clinics will be pooled for analyses.^{316,317} All analyses will be done using the most recent version of SAS, SPSS, R or M-Plus.³¹⁵⁻³²² Demographic variables (age, gender, race, ethnicity, family structure, marital status, SES) and baseline values of primary and secondary end points, and questionnaire results will be summarized by group. If the normality assumption holds, t-tests of continuous baseline variables and Fisher exact test/chi-square test/CMH test for categorical variables will be used to compare the TC and UC groups at baseline; one-way ANOVA will be used for comparisons of secondary groups. The statistician will select analytic methods based on data distributions and any imbalanced baseline scores.³²³ Linear mixed effects modeling (continuous outcomes) or generalized linear mixed modeling (categorical outcomes) is planned for the hypotheses below.³¹⁵⁻³²² Treatment group (UC vs TC) and demographic characteristics will be fixed effects in these models, while site, physician, and within-subject effects will be random effects. The same analyses will be attempted for secondary groups, sample size permitting. We will use Holmbeck's methods³²⁴ to evaluate baseline demographic variables and questionnaire scores as moderators of TC-UC effects on primary outcomes and to evaluate mediation of effects on primary endpoints. Candidate mediators are variables that are obtained serially concurrent with the primary endpoints at ≥ 3 visits.

Sample Size and Statistical Power: Recruitment ended at the end of March 2020. A total of 115 families were recruited. Allowing for some attrition prior to randomization, a sample of 100 patients (65 TC and 35 UC) yields 87.4% power to detect a clinically meaningful group differences in mean HbA_{1c} of 0.5% (~0.7 SD) versus the alternative of equal means using a t test with $p = .05$. Limiting recruitment to those with HbA_{1c} = 7.5-10.0% is anticipated to reduce the SD from 1.5% for the general adolescent T1D population to 0.7%, boosting effective statistical power for the RCT. The predicted 12-month means are 8.1% (TC) and 8.6% (UC). If the SD is 1.0%, our power is reduced to 71.3%; if it is 1.5% as in the general population, our power is 50.9%. This sample size also achieves power of 78.2% to detect a clinically meaningful mean differences in the DSMP-SR

total score of 7.0 points (~0.6 SD) at 1 year. The estimated mean values are 63.0 (TC) and 56.0 (UC). This preliminary trial will yield rich data that could be used to guide the sampling plan for a future, more ambitious, multi-center trial.³²⁵⁻³²⁷ The following hypotheses will be tested:

Hypothesis 1: Compared with UC patients, those randomized to TC will have significantly more favorable primary (HbA_{1c} and DSMP-SR scores) and secondary (frequency of severe hypoglycemia and level of glycemic variability) diabetes management outcomes at their 6, 9, and 12 month follow-up visits.

Hypothesis 2: Compared with UC patients, those randomized to TC will demonstrate more favorable scores on the T1DAL, PAID, and CPI at follow-up measurements.

Hypothesis 3: Significantly higher scores will be obtained on the DCI completed by HCPs describing TC care compared to HCPs describing UC care.

Hypothesis 4: Effects of TC on HbA_{1c} and DSMP-SR scores will be moderated by demographic variables (youth age, family SES, # of adult caregivers in the home) and by baseline scores on the T1DAL, PAID, and CPI. More benefit from TC will accrue to youth who are younger, from two-parent families with higher SES, and with more favorable scores on the T1DAL, PAID and CPI.

Hypothesis 5: Effects of TC on HbA_{1c} and DSMP-SR scores will be mediated by changes in scores on the T1DAL, PAID, and CPI. More benefit from TC will accrue to youth with favorable changes in T1DAL, PAID and CPI scores during the 12 months of the study.

[figure not shown]
Hypothesis 6: TC-TH adolescents will keep significantly more appointments than either TC-IP or UC youths.

Limitations: Aspects of this application could have been done differently: 1.) Randomization at the level of patients/families was selected over randomizing sites in a Cluster RCT design. A Cluster RCT could reduce the potential for contamination, but it introduces problems in that differences between Nemours sites could obscure detection of treatment effects. We opted for randomization of patients/families to treatments with concomitant efforts to minimize possible contamination. Since this funding mechanism seeks to develop preliminary data to support a larger multi-site RCT in the future, empirical evaluation of our success in detecting, preventing and managing possible contamination effects would be an important feature of a future application of that type. 2.) The original structure of the RCT as a 3-arm trial (UC vs TC-IP vs TC-TH) introduces added complexity and expense and may decrease the sample size available for each study arm. Since telehealth delivery of subspecialty care for chronic conditions may be the wave of the future, it is prudent to capitalize on the availability of the DP3 mechanism to provide initial data on if and how telehealth delivery of the proposed TC intervention may be superior to conventional face to face delivery of that same care. Unfortunately, precautions due to COVID-19 spread has limited the TC-IP arm of the trial but comparisons are possible between UC and TC-TH as originally planned. 3.) The enrolled sample represents a period of marked developmental change. We have not planned specific adaptations to the TC model, but a key role of the Psychology Post-Doctoral Fellow will be assurance that negotiated interventions are developmentally appropriate for each adolescent.

Time Frame: The first few months of the 36 month study period will include hiring/assigning project staff, writing a procedure manual, obtaining IRB approval, constituting the Parent, Adolescent and HCP Crowds and starting qualitative interviews of stakeholders. Qualitative analyses of stakeholder responses to crowdsourcing questions will continue through month 6, and we will then ensure that themes derived from those analyses are reflected in planning of the TC model and in training the TC HCPs. TC training will begin at month 6 and continue for about 6 months, during which the teams will practice the TC model with simulated parent-adolescent dyads and several study-ineligible dyads. Recruitment and data collection for the RCT will begin near the end of Year 1 and will continue until the midpoint of Year 3. Statistical analysis of RCT results, cost-effectiveness analyses, post-study qualitative interviews of parents, adolescents, HCPs and other stakeholders and dissemination of study results will occur during the latter half of Year 3.

3.5. OVERALL IMPACT Conventional multidisciplinary care for T1D in adolescents is not meeting their needs and it is not yielding acceptable health or psychological outcomes. A fresh look at how care is delivered to this population, careful user-centered design of an alternative model of care and rigorous testing of a well-

articulated transdisciplinary care model will set the stage for a definitive multi-site randomized clinical trial. The proposed work could change how adolescents with T1D receive health care by rigorously validating a novel, manualized model of care that applies evidence-based assessment and intervention methods targeting known psychosocial mechanisms. Figure 2 illustrates that the TC model is designed to shift the center of the HbA_{1c} distribution to the left by helping adolescents achieve clinically significant improvement in glycemic control. The TC model could yield a substantial return on investment in improved health and quality of life, efficient use of scarce human resources, reduction of excess health care use, and lower costs, and the findings may apply to other pediatric chronic conditions.

4. INCLUSION AND ENROLLMENT REPORT (Not Applicable)

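### The delivery-mode models use post-March-2020 labels on which TC-TH versus TC-IP is not a randomised contrast, and Hypothesis 6 does not say which TC-IP it means

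*Combined protocol and SAP*

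**What the plan says.** All references are to section 3.4 of the combined protocol and SAP. Experimental Design randomises families to TC-IP, TC-TH or UC, 50 per arm as planned.

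The subsection on COVID-19 changes reports the position in March 2020: "About one third of the families randomly assigned to TC-IP had completed the study". The rest of that arm could not finish in person and was given two new labels. The first, TC-IP/TH, is for families already part way through: "Families who had already received some TC-IP visits were transitioned to receiving TC through telehealth and were reclassified as" (the label follows in the text). The second, TC-TH/CH, is for families not yet seen in person: "Those randomized to TC-IP who had received no TC-IP visits but were due for clinical care also received TC through telehealth"; they may later choose their mode. Families randomised to TC-TH are not relabelled. All TC groups are pooled for the primary comparison with UC. On delivery mode the subsection says "comparisons will be made between the TC groups (size permitting) to explore whether delivery mode is important for outcomes". It also notes a change in the control arm: "UC appointments are, for now, also being delivered through telehealth".

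The Analytic Plans summarise data by UC and TC and by "secondary group (TC-TH, TC-IP, TC-IP/TH, TC-TH/CH"). For the main models, "Treatment group (UC vs TC) and demographic characteristics will be fixed effects in these models", with site, physician and within-subject random effects. The same models are to be tried on the secondary groups if numbers allow. Secondary group also appears among the exploratory subgroups: "Exploratory subgroup analyses (e.g. race, ethnicity, gender, SES, secondary group) will be conducted as needed".

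Hypothesis 6 predicts that TC-TH youths keep more appointments than TC-IP or UC youths. It does not define TC-IP. Hypotheses 1 and 2, by contrast, refer expressly to those randomised to TC.

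**The concern.** TC-IP carries two meanings. In Experimental Design it is a randomised arm. In the Analytic Plans it stands beside TC-IP/TH and TC-TH/CH, so there it can only be what is left of the arm once those families are removed.

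Membership of that remainder depends on how early a family enrolled and on visits received after randomisation. TC-TH has been through no such filter. Comparing the two sets early families, seen before the switch, against a mixture of early and late families seen in both periods. The model terms that the plan names include no calendar period.

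Hypothesis 6 leaves the choice open, so two analysts could each follow the plan and compare TC-TH with different families. A difference could then appear, or be hidden, without any effect of delivery mode. The mode results matter because Specific Aim 2 would use them to explore whether telehealth delivery should be evaluated in later trials.

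**Working it through.** The plan gives no sample size or power for any mode contrast, so there is no figure to reproduce. Its HbA1c power (87.4%) is for pooled TC versus UC. The stated inputs (65 and 35 families, difference 0.5%, SD 0.7%, two-sided 5% t test) give 92.1%. That is a separate matter, and nothing below depends on it.

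**1. The labels set against the arms.**

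| Randomised arm | Position at the switch | Label in the Analytic Plans |
|---|---|---|
| TC-IP | finished, about 1/3 | TC-IP |
| TC-IP | some in-person visits | TC-IP/TH |
| TC-IP | none yet, due for care | TC-TH/CH |
| TC-TH | any | TC-TH |

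**2. Numbers.** The current TC-IP/TC-TH split is not given. Assume that the 65 TC families divide 33 TC-TH and 32 TC-IP. The TC-IP label then holds 32/3, about 11 families, and about 21 carry other labels. By label the contrast is 33 versus about 11; by arm it is 33 versus 32.

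**3. Share of TC-TH appointments after the switch.** Assume even entry over E months up to March 2020 and 12 months of follow-up.
- (E − 12)/E = 1/3 gives E = 18 months.
- For visits at 3, 6, 9 and 12 months, the share before the switch is mean(15, 12, 9, 6)/18 = 10.5/18 = 0.583. The share after it is 0.417.
- For the TC-IP label the share after the switch is 0.
- If 30% or 37% had finished, the TC-TH share after the switch is 0.44 or 0.39. With one third finished but entry falling or rising linearly towards March 2020, it is 0.31 or 0.44.

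**4. Bias from calendar period alone, appointments kept.** Bias = 0.417 × period change in attendance.
- No change gives 0. An assumed change of ±10 points gives ±4.2 points.
- Simulation with no mode effect used mean attendance of 75% or 85%, beta-distributed family rates (concentration 4 or 10) and period changes of −10, 0 and +10 points. The label contrast shifted by −4.3 to +3.9 points, with a standard error of 7.1 to 10.0.
- 4.2/10.0 = 0.42 and 4.2/7.1 = 0.59, so the shift is about half a standard error.
- The contrast by randomised arm stayed within 0.3 points of zero.

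**5. Bias from enrolment date, continuous outcomes.** Suppose early families differ from later ones by s standard deviations. TC-TH is one third early and the TC-IP label is all early, so the contrast shifts by (2/3)s. For s = 0.25 this is 0.17 SD and for s = 0.5 it is 0.33 SD. A nominal 5% test then rejects in 7% and 14% of simulated trials with no mode effect, against 4 to 5% by randomised arm. The values of s are assumptions; the documents support no particular one.

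**The case against.** The strongest reply is that Hypothesis 6 most naturally means the arm. TC-IP was defined as an arm, and text written after the switch, both in the COVID-19 subsection and under Limitations, still uses the name that way. On that reading Hypothesis 6 needs only a clarifying phrase. This stands. A reader might infer that Hypothesis 6 is non-randomised as written, but the documents do not settle which meaning applies.

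Second, it is an inference that the TC-IP label is exactly the families who had finished. The text does not place families who withdrew, or those with no visit who were not yet due. Figure 2, not shown in the text available, may define the labels or give counts. That is why the point says mainly. A reader might also suppose that the label selects good attenders; this is possible, but nothing in the documents shows or sizes it.

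Third, the mode models are called exploratory and depend on numbers. Limitations says that the TC-IP arm was curtailed and vouches only for UC versus TC-TH. Tracking mode received also serves the stated interest in feasibility and family preference. This lowers the stakes, but neither an exploratory label nor a note of curtailment tells the reader that a comparison has lost randomisation. Hypothesis 6 is, moreover, listed among the hypotheses to be tested.

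Fourth, the illustrated period bias is small beside the sampling error. That is true for attendance under these assumptions.

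**Conclusion.** The concern holds in a limited form. As written, the Analytic Plans run the mode models on labels for which TC-TH versus TC-IP is not randomised and mixes mode with enrolment date and calendar period. Hypothesis 6 has the same problem only on one of its two readings.

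Three stronger conclusions are not supported:
- That the main results are compromised. Pooled TC versus UC and TC-TH versus UC keep their randomised groups.
- That the bias favours telehealth, or is large. Neither sign nor size can be established. The figure of about 4 attendance points needs an assumed 10-point period change, even entry and an assumed 33/32 split.
- That the mode results will decide the future of telehealth delivery. Specific Aim 2 speaks only of exploring this.

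The definition should be fixed before analysis, so that the TC-IP group is not chosen with results in view.

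**What to change.** 1. **Hypothesis 6.** Define TC-TH, TC-IP and UC as the arms as randomised. Compare TC-TH with TC-IP on the proportion kept of appointments scheduled before the March 2020 switch, with all scheduled appointments as a sensitivity analysis.
2. **Other outcomes.** Make the exploratory mode comparison by randomised arm, stating that the switch dilutes it. Report the four labels descriptively, marked as non-randomised.

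This is SAP wording. No new data are needed, because Table 3 records appointment keeping at every quarterly visit.

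**Cost for Hypothesis 6.** Under even entry about 42% of appointments drop out, leaving 33 × 4 × 0.583 = 77 in TC-TH and 32 × 4 × 0.583 = 75 in TC-IP. Power for an assumed 15-point mode effect, as Φ(effect/SE − 1.96) with the simulated standard errors:
- By arm, before the switch: SE 6.3 to 8.7, power 66% to 41%.
- By arm, all appointments: effect diluted to 15 × 0.583 = 8.75 points if no visits were in person after the switch; SE 4.5 to 7.1, power 49% to 23%.
- By label: SE 7.1 to 10.0, power 56% to 32%, without the protection of randomisation.

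This favours the pre-switch analysis as the main one.

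**Cost for HbA1c.** Take a true 0.5% effect, SD 0.7% and 33 versus 32 families. If month-12 HbA1c reflects the share of visits made in person, the effect is 0.5 × 0.583 = 0.29% and power is 38%. If it follows only the mode in use at month 12, the effect is 0.5 × 1/3 = 0.17% and power is 16%. The label contrast (33 versus 11, undiluted) would have 52%, but it is not randomised. The mode comparison is weak by either route, and the report should say so.
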